5.4.3 Dose Reductions

Dose reductions may be allowed in the event that observed AEs are believed to be related to study drug, and which in consultation between the Investigator and the Medical Monitor, may be managed by a 50% reduction in dose. The duration of the dose reduction will be at the Investigator's discretion.

5.5 TREATMENT COMPLIANCE

Treatment compliance will be documented in the eCRF by recording the date, time, and whether or not each IV dose of study drug was completely infused.

5.6 PRIOR AND CONCOMITANT MEDICATION/THERAPY

Prior and concomitant medications include any drug (prescription or over-the-counter) or biological product (such as vaccines, blood or blood components) including herbal remedies or preparations. All prior/concomitant medications taken or received by a subject within the 28 days prior to the Month 1-Day 1 Visit through the EOS Visit, and any changes to concomitant medications during the study will be recorded in the appropriate eCRF. In addition, all prior therapies for AL amyloidosis taken prior to signing ICF for this study and since last visit in Study NEOD001-001 will be recorded. See Study Manual for more information.

5.6.1 Allowed Concomitant Medication/Therapy

The following are allowed during the study:

- Radiation therapy for the removal of local amyloid deposits
- Concomitant chemotherapy
 - The Investigator may prescribe chemotherapy as per standard of care
 - Particular care must be taken to accurately report chemotherapy administration, including missed or delayed doses, and dose reductions
 - If parenteral chemotherapy is administered on the same day as NEOD001, the chemotherapy must be administered after the 90-minute NEOD001 observation period
 - Within 3 days before the first day of a new regimen of chemotherapy, conduct an unscheduled central laboratory collection (including hematology, chemistry, PT/INR, and PTT)
 - Routine medications should not be administered in the 15 minutes after the completion of the NEOD001 infusion. Medications such as anti-emetics required for prophylaxis of emesis for the subsequent chemotherapy should be given after the ECG has been done.

5.6.2 Prohibited Concomitant Medication/Therapy

The following are not allowed during the study:

- Other investigational agents

- Myeloablative chemotherapy with ASCT
- Gadolinium contrast agents are only permitted in exceptional circumstances. If a subject requires the use of gadolinium contrast agents, contact the Medical Monitor.

6 **STUDY PROCEDURES**

6.1 **EVALUATIONS BY VISIT**

6.1.1 **Screening Period: Days -28 to -1**

A signed ICF must be obtained before any study-specific screening evaluations are performed and should be documented in the subject's medical chart.

Screening evaluations and procedures will be performed within 28 days prior to the first study drug administration on Month 1-Day 1.

Rescreening is allowed once per subject. Repeat only tests that did not meet eligibility requirements. All laboratory evaluations to be done centrally, unless otherwise noted. Refer to the Central Laboratory Manual for complete instructions on collection of samples.

6.1.1.1 **Assessments for Subjects Whose Previous Visit in Study NEOD001-001 was Within 60 Days of Screening**

- Signed informed consent
- Review eligibility, including discontinuation of prior therapies according to the Exclusion Criteria
- Medical History - Obtain medical history since subject's last visit in Study NEOD001-001 (including all major hospitalizations and surgeries), as well as the subject's current medical status and prior therapies for AL amyloidosis. Adverse events that resolved prior to the subject's last visit in Study NEOD001-001 and prior to signing ICF for this study should be assessed as possible medical history in this study.
- Historical NT-proBNP levels – any NT-proBNP results available since participation in Study NEOD001-001 must be recorded
- Prior and concomitant medications/therapy (per Section 5.6)
- Assessment of AEs; record any AEs that were ongoing from the subject's last visit in Study NEOD001-001 and at the time of the NEOD001-OLE001 Screening Visit
- Complete physical examination - including height, weight, and examination of general appearance; head, ears, eyes, nose, and throat; neck; skin; cardiovascular system; respiratory system; abdominal system; and nervous system. The following should be assessed: macroglossia, submandibular nodes/fullness, adenopathy, ecchymoses, liver/spleen size (palpable +/-), ascites (+/-), and edema (which should be quantified on a scale of 0-4).
- Vital signs including heart rate (HR), BP, respiratory rate (RR), and body temperature (Section 6.3.2)
 - Note: subjects with uncontrolled hypotension or systolic BP <85 mmHg are not eligible for the study

- Peripheral Neuropathy Assessment (Section 6.3.5 and Appendix 5)
 - Note: only for subjects previously enrolled in Cohort C of Study NEOD001-001
- SF-36 Health Survey (Appendix 2)
 - Note: administer SF-36 before performing any other study assessments on the day it is administered
- 6MWT (Section 6.3.6): Two pretreatment 6MWTs are required before the first administration of study drug, with a minimum of 4 days in between the two tests. The second test must be completed 1 to 2 days before the Month 1-Day 1 Visit. Also collect HR and BP pre- and post-6MWT administration.
 - Note: NT-proBNP must be drawn before conducting 6MWT, if performed on the same calendar day
- 12-lead ECG in triplicate (perform locally)
- Laboratory Assessments:
 - Hematology, chemistry (including amylase), and Screen for Infectious Diseases per Appendix 3
 - Coagulation per Appendix 3; collect unscheduled citrated plasma samples for subjects with relevant SAEs; if defects are identified, additional analytes will be analyzed, as indicated (see Appendix 4)
 - Cardiac biomarkers per Appendix 3
 - Serum pregnancy tests (WOCBP only): Perform a serum pregnancy test (central) within 28 days before Month 1-Day 1 study drug administration
- Other Assessments (see Laboratory Manual):
 - Serum NEOD001 concentration
 - Serum anti-NEOD001 antibodies

6.1.1.2 Assessments for Subjects Whose Previous Visit in Study NEOD001-001 was ≥60 Days from Screening

- Signed informed consent
- Begin urine collection 24 hours prior to the study visit
- Review eligibility, including discontinuation of prior therapies according to the Exclusion Criteria

- Medical History - Obtain medical history since subject's last visit in Study NEOD001-001 (including all major hospitalizations and surgeries), as well as the subject's current medical status and prior therapies for AL amyloidosis. Adverse events that resolved prior to the subject's last visit in Study NEOD001-001 and prior to signing ICF in this study should be assessed as possible medical history in this study.
- Historical NT-proBNP levels – any NT-proBNP results available since participation in Study NEOD001-001 must be recorded
- Prior and concomitant medications/therapy (per Section 5.6)
- Assessment of AEs; record any AEs that were ongoing from the subject's last visit in Study NEOD001-001 and at the time of the NEOD001-OLE001 Screening Visit.
- Complete physical examination - including height, weight, and examination of general appearance; head, ears, eyes, nose, and throat; neck; skin; cardiovascular system; respiratory system; abdominal system; and nervous system. The following should be assessed: macroglossia, submandibular nodes/fullness, adenopathy, ecchymoses, liver/spleen size (palpable +/-), ascites (+/-), and edema (which should be quantified on a scale of 0-4).
- Vital signs including HR, BP, RR, and body temperature (Section 6.3.2)
 - Note: subjects with uncontrolled hypotension or systolic BP <85 mmHg are not eligible for the study
- ECOG PS (Appendix 6)
- New York Heart Association (NYHA) functional status (Appendix 7)
- Peripheral Neuropathy Assessment (Section 6.3.5 and Appendix 5)
 - Note: only for subjects previously enrolled in Cohort C of Study NEOD001-001
- SF-36 Health Survey (Appendix 2)
 - Note: administer SF-36 before performing any other study assessments on the day it is administered
- 6MWT (Section 6.3.6): Two pretreatment 6MWTs are required before the first administration of study drug, with a minimum of 4 days in between the two tests. The second test must be completed 1 to 2 days before the Month 1-Day 1 Visit. Also collect HR and BP pre- and post-6MWT administration.
 - Note: NT-proBNP must be drawn before conducting 6MWT, if performed on the same calendar day
- Echocardiogram

- 12-lead ECG in triplicate (perform locally)
- Laboratory Assessments:
 - Hematology and chemistry (including amylase) per [Appendix 3](#)
 - Coagulation per [Appendix 3](#); collect unscheduled citrated plasma samples for subjects with relevant SAEs; if defects are identified, additional analytes will be analyzed, as indicated (see [Appendix 4](#))
 - Cardiac biomarkers per [Appendix 3](#)
 - Serum pregnancy tests (WOCBP only): Perform a serum test (central) within 28 days before Month 1-Day 1 study drug administration
 - Serum free light chain (SFLC)
 - Serum protein electrophoresis (SPEP) and 24-hour urine protein electrophoresis (UPEP)
 - Serum immunofixation (SIFE) and urine immunofixation (UIFE)
 - Urinalysis (dip stick) per [Appendix 3](#)
 - 24-hour urine protein excretion
- Other Assessments (see Laboratory Manual):
 - Serum NEOD001 concentration
 - Serum anti-NEOD001 antibodies

6.1.2 Treatment Period: Months 1 through 36, Day 1 (± 5 Days)

Day 1 assessments may be conducted ± 5 days from Day 1, with the exception of Month 1-Day 1 (i.e., no window is allowed at Month 1).

Subjects will receive 24 mg/kg of NEOD001 as an IV infusion every 28 (± 5) days, i.e., on Day 1 of Months 1 through 36.

All laboratory tests to be done centrally, unless otherwise noted. Refer to the Central Laboratory Manual for complete instructions on collection of samples.

Although central laboratory assessments will be performed each month for study analysis, local laboratory assessments including hematology, chemistry, and urinalysis will be performed for subject management. Results will be reviewed prior to dosing at each month's Day 1 visit to confirm that continued dosing is appropriate.

Subjects who present with symptomatic orthostatic hypotension or systolic BP <85 mmHg, which in the medical judgment of the Investigator would interfere with the subject's ability to safely receive treatment, will have the study drug withheld. If the study drug is withheld and subsequently rescheduled, central laboratory assessments required for that visit will need to be repeated if they were drawn >7 days prior to the rescheduled dosing date. However, a symptom-directed physical examination and vital signs need to be repeated prior to each dosing.

An unscheduled central laboratory collection (i.e., hematology, chemistry, PT/INR, and PTT) will be conducted within 3 days before the first day of a new regimen of chemotherapy.

Prior to Infusion:

The following assessments will be done prior to study drug administration on Day 1 of every month, unless otherwise indicated. Because questionnaires and laboratory samples should be completed prior to the 6MWT, all of the following assessments, at a minimum, should be completed 1 to 2 days prior to Day 1:

- Begin urine collection 24 hours prior to the study visit
- Concomitant medications/therapies
- Assessment of AEs
- Directed physical examination - including weight and examination of the following: general appearance; head, ears, eyes, nose, and throat; neck; skin; cardiovascular system; respiratory system; abdominal system; and nervous system. The components of the physical examination will be as clinically indicated. However, at all time points the following should be assessed: macroglossia, submandibular nodes/fullness, adenopathy, ecchymoses, liver/spleen size (palpable +/-), ascites (+/-), and edema (which should be quantified on a scale of 0-4).
- Vital signs including HR, BP, RR, and body temperature; assess in the same position for all time points (Section 6.3.2)
- ECOG PS (Appendix 6)
- NYHA functional status (Appendix 7)
- Peripheral Neuropathy Assessment (Section 6.3.5 and Appendix 5) – every 3 months
 - Note: only for subjects previously enrolled in Cohort C of Study NEOD001-001
- SF-36 Health Survey (Appendix 2) – every 6 months
 - Note: administer SF-36 before performing any other study assessments on the day it is administered

- 6MWT (Section [6.3.6](#)) – every 6 months; also collect HR and BP pre- and post-6MWT administration
 - Notes: NT-proBNP must be drawn before conducting 6MWT, if performed on the same calendar day. The 6MWT must be performed 1-2 days prior to administration of study drug; it should not be administered on the same day as study drug administration (i.e., Day 1).
- Echocardiogram – every 12 months
 - Note: May be conducted within 10 days before the visit
- 12-lead ECG in triplicate (perform locally) – every 3 months
- Laboratory Assessments:
 - Hematology and chemistry (including amylase) per [Appendix 3](#)
 - Coagulation per [Appendix 3](#); collect unscheduled citrated plasma samples for subjects with relevant SAEs; if defects are identified, additional analytes will be analyzed, as indicated (see [Appendix 4](#))
 - Cardiac biomarkers per [Appendix 3](#)
 - Urine pregnancy test (WOCBP only; local laboratory) – Monthly starting with Month 2
 - SFLC – every 3 months
 - SPEP and 24-hour UPEP – every 3 months
 - Note: During the Treatment Phase, SPEP and UPEP are used to confirm the initial within-study hematologic complete response only
 - SIFE and UIFE – every 3 months
 - Note: During the Treatment Phase, SIFE and UIFE are used to confirm the initial within-study hematologic complete response only
 - Urinalysis (dip stick) per [Appendix 3](#) – every 3 months
 - 24-hour collection for urine protein excretion – every 3 months
- Other Assessments (Laboratory Manual) – every 3 months
 - Serum NEOD001 concentration
 - Serum anti-NEOD001 antibodies

- Additional samples for anti-NEOD001 antibodies and serum NEOD001 should be collected if a significant toxicity is observed

NEOD001 Administration:

Note: Subjects who present with symptomatic orthostatic hypotension or systolic BP <85 mmHg will have the study drug held

- Month 1-Day 1:
 - Administer NEOD001 IV using the infusion duration established during Study NEOD001-001 or over 60 (± 10) minutes (Section 5.3)
 - Assess vital signs including HR, BP, RR, and body temperature, halfway through the infusion (Section 6.3.2)
- All Other Months:
 - If the Month 1-Day 1 infusion was well tolerated without infusion-associated AEs, administer NEOD001 IV using the infusion duration established during Study NEOD001-001 or over 60 (± 10) minutes. If needed, see Section 5.4 for dose adjustment instructions.

After Infusion:

- Monitor subjects for 90 (± 10) minutes following completion of the study drug infusion. Beginning with the third infusion, the Investigator may decrease the postdose monitoring time to no less than 60 minutes, if no infusion-related reactions were observed in the previous infusions and allowed per the IRB/IEC (per Section 5.3). The Investigator may increase the monitoring time if deemed appropriate or per local standards. In the event of any clinical concerns or suspicious signs or symptoms after the infusion, the subject will remain under observation for as long as the Investigator deems it appropriate.
- Routine medications should not be administered in the 15 minutes after the completion of the NEOD001 infusion
- Vital signs including HR, BP, RR, and body temperature (Section 6.3.2):
 - Month 1-Day 1:
 - Immediately at end of infusion (EOI) (+5 minutes)
 - 30 (± 5) minutes after EOI
 - 60 (± 10) minutes after EOI
 - All Other Months:
 - Immediately at EOI (+5 minutes)

- 60 (\pm 10) minutes after EOI
- 12-lead ECG in triplicate (perform locally)
 - Within 15 minutes after EOI
- Serum NEOD001 concentration – every 3 months
 - EOI (record the time, but the sample can be collected at any time after the infusion on Day 1)
- Discharge subject from clinic if no immediate safety concerns and/or hypersensitivities are present after the postdose assessments and observation period. In the event of any clinical concerns or suspicious signs or symptoms after the infusion, the subject will remain with the Investigator and study staff for further observation until the Investigator deems the subject can safely leave the clinic.

6.1.3 End of Study (EOS): 30 (\pm 5) Days After Final Dose

A final visit should be scheduled 30 (\pm 5) days after the last administration of NEOD001. The following procedures must be conducted:

- Begin urine collection 24 hours prior to the study visit
- Concomitant medications/therapy
- Assessment of AEs
- Complete physical examination - including weight and examination of general appearance; head, ears, eyes, nose, and throat; neck; skin; cardiovascular system; respiratory system; abdominal system; and nervous system. The following should be assessed: macroglossia, submandibular nodes/fullness, adenopathy, ecchymoses, liver/spleen size (palpable +/-), ascites (+/-), and edema (which should be quantified on a scale of 0-4).
- Vital signs including HR, BP, RR, and body temperature (Section 6.3.2)
- ECOG PS (Appendix 6)
- NYHA functional status (Appendix 7)
- Peripheral Neuropathy Assessment (Section 6.3.5 and Appendix 5)
 - Note: only for subjects previously enrolled in Cohort C of Study NEOD001-001
- SF-36 Health Survey (Appendix 2)
 - Note: administer SF-36 before performing any other study assessments on the day it is administered

- 6MWT (Section 6.3.6); also collect HR and BP pre- and post-6MWT administration
 - Note: NT-proBNP must be drawn before conducting 6MWT, if performed on the same calendar day
- Echocardiogram
 - Note: repeat echocardiogram at EOS if not performed within 60 days prior to visit
- 12-lead ECG in triplicate (perform locally)
- Laboratory Assessments:
 - Hematology and chemistry (including amylase) per [Appendix 3](#)
 - Coagulation per [Appendix 3](#); collect unscheduled citrated plasma samples for subjects with relevant SAEs; if defects are identified, additional analytes will be analyzed, as indicated (see [Appendix 4](#))
 - Cardiac biomarkers per [Appendix 3](#)
 - Serum pregnancy test (WOCBP only; central laboratory)
 - SFLC
 - SPEP and 24-hour UPEP
 - SIFE and UIFÉ
 - Urinalysis (dip stick) per [Appendix 3](#)
 - 24-hour urine protein excretion
- Other Assessments (see Laboratory Manual):
 - Serum NEOD001 concentration
 - Serum anti-NEOD001 antibodies
 - Additional samples for anti-NEOD001 antibodies and serum NEOD001 should be collected if a significant toxicity is observed

6.1.4 90-day Postdose Pregnancy Test

For WOCBP only: Obtain a local laboratory serum pregnancy test 90 (± 5) days after the last administration of study drug.

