Peripheral Neuropathy Assessment ⁹	X	X	Every 3 months ¹⁰	X
SF-36 Health Survey ¹¹	X	X	Every 6 months ¹²	X
6MWT ¹³	X ¹⁴	X ¹⁴	Every 6 months ¹²	X
Echocardiogram		X	Every 12 months ¹⁵	X ¹⁶
ECG (12-lead in triplicate; local)	X	X	Every 3 months ^{10,17}	X
Vital Status Telephone Call				Every 3 months ¹⁸
Laboratory²¹				
Hematology & Chemistry ¹⁹	X	X	X	X
Amylase	X	X	X	X
Coagulation ²⁰	X	X	X	X
Troponin T	X	X	X	X
NT-proBNP ¹³	X	X	X	X
Pregnancy (WOCBP) ²²	X	X	X	X, X ²³
Serum Free Light Chain		X	Every 3 months ¹⁰	X
SPEP & 24-hour UPEP ²⁴		X	Every 3 months ^{10,25}	X
SIFE & UIFE		X	Every 3 months ^{10,25}	X
Urinalysis (dip stick) ²⁶		X	Every 3 months ¹⁰	X
24-hr Urine Protein Excretion ²⁴		X	Every 3 months ¹⁰	X
Other				
Serum NEOD001 Sample ²⁷	X	X	Every 3 months ¹⁰	X
Serum anti-NEOD001 Antibody Sample ²⁸	X	X	Every 3 months ¹⁰	X
NEOD001 Infusion ²⁹			X	

ECG = electrocardiogram; ECOG PS = Eastern Cooperative Oncology Group performance status; EOI = end of infusion; EOS = End of Study; INR = international normalized ratio; NT-proBNP = N-terminal pro B-type natriuretic peptide; NYHA = New York Heart Association; PK = pharmacokinetic; PT = prothrombin time; PTT = partial thromboplastin time; SF-36 = Short form-36; SIFE = serum immunofixation electrophoresis; 6MWT = 6-Minute Walk Test; SPEP = serum protein electrophoresis; UIFE = urine immunofixation electrophoresis; UPEP = urine protein electrophoresis; WOCBP = women of childbearing potential.

1. Rescreening is allowed once per subject. Only repeat tests that did not meet eligibility requirements.
2. Day 1 assessments may be conducted ±5 days from Day 1, with the exception of Month 1-Day 1 (i.e., no window is allowed at Month 1).

3. Conduct the EOS Visit 30 (± 5) days after last administration of study drug. Two additional evaluations are to be conducted beyond this time point, see Footnotes 18 and 23.
4. Obtain medical history since subject's last visit in Study NEOD001-001 (including all major hospitalizations and surgeries), as well as the subject's current medical status and prior therapies for AL amyloidosis. Adverse events that resolved prior to the subject's last visit in Study NEOD001-001 and prior to signing the ICF for this study should be assessed as possible medical history in this study.

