6.1.5 Vital Status Telephone Call

Conduct a vital status telephone call approximately 3 months after the subject's last study visit and approximately every 3 months thereafter for up to 5 years, death, or subject withdraws consent, whichever occurs first.

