The reporting period for AEs is from the time that the ICF is signed through 30 days after the last dose of study drug or last study visit, whichever is later. All AEs, whether or not related to the study drug, must be fully and completely documented in the eCRF and in the subject's medical notes. The following attributes must be assigned: description, dates of onset and resolution, severity, assessment of relatedness to study drug (either related or not related), and action taken. The Investigator may be asked to provide additional follow-up information.

In the event that a subject is withdrawn from the study because of an AE, it must be recorded in the eCRF. The subject should be followed and treated by the Investigator until the AE has resolved, stabilized, or a new chronic baseline has been established.

The Investigator must report all AEs. At each visit the Investigator will ask the subject a nonspecific question (e.g., "Have you noticed anything different since your last visit?") to assess whether any AEs have been experienced since the last report or visit. AEs will be identified and documented in the eCRF in appropriate medical terminology. The severity and the relationship to the study drug will be determined and reported in the eCRF (see Sections 7.2 and 7.3).

Note that any intermittent or as-needed ("PRN") use of medication (and specifically any newly prescribed medication) during the course of a study may indicate the occurrence of an AE that may need to be recorded on multiple eCRFs (e.g., AE and Concomitant Medication eCRFs).

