The reporting period for SAEs is the period from signing of the ICF through 30 days after the last administration of study drug or last study visit, whichever is later. SAEs reported to the Investigator outside of this reporting period will be reported to the Sponsor or its designee if, in the judgment of the Investigator, there is “a reasonable possibility” that the event may have been caused by the product.

All SAEs will continue to be followed until the end of the study or until such events have resolved or the Investigator, in conjunction with the Sponsor or its designee, deems them to be chronic or stable.

8 **STATISTICAL METHODS AND CONSIDERATIONS**

The final analyses will be based on all subject data collected through study discontinuation.

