9.2. Adverse Events

Verbatim terms on the OLE Adverse Event eCRFs will be mapped to PT and SOC using MedDRA version 19.0. AEs will be reported and severity will be categorized using the Common Terminology Criteria for Adverse Events (CTCAE, Version 4.03).

AE summaries will use the OLE Safety Population.

All AE summaries will be restricted to treatment-emergent adverse events (TEAEs), which are defined as any AE that newly appears, increases in frequency, or worsens in severity following initiation of study drug and up to 30 days after date of last dose or last study visit, whichever is later. If it cannot be determined whether the AE is treatment emergent due to a partial onset date, then it will be counted as such.

Each AE summary will be displayed by treatment group. Summaries that are displayed by SOC and PT will be ordered by descending order of NEOD001-OLE001 24 mg/kg incidence of SOC and PT within each SOC.

The following listings will be presented by subject, with non-TEAEs flagged:

- All AEs
- Serious adverse events (SAEs) (this is a subset of the AEs where serious is marked as “Yes”)
- CTCAE Grade 3 or higher AEs (this is a subset of AEs where severity is missing or marked as CTCAE Grade 3, 4, or 5)
- Related AEs (this is a subset of the AEs where relationship marked as “Related” or relationship is missing)
- AEs leading to Study Drug Withdrawal (this is a subset of the AEs where Action Taken with Study Treatment is checked as “Drug Discontinued”)
- Fatal AEs (this is a subset of the AEs where outcome is indicated as “Fatal” or the CTCAE grade is 5)
- AEs resulting in any dose change (i.e., interruption, reduction, held, or prolongation)
- AEs assessed by the investigator as infusion-associated (this is a subset of the AEs where infusion-associated AE was reported as "Yes.")
- AEs within one day of any infusion (this is a subset of the AEs where AE onset date was the same day as the date of any infusion)

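### An EOS visit on days 25 to 29 leaves the last 1 to 5 days of the AE reporting period without a scheduled AE question

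*Protocol*

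**What the plan says.** **Timing of the last visit.** Protocol 6.1.3: "A final visit should be scheduled 30 (\pm 5) days after the last administration of NEOD001". The same ±5-day window stands in the synopsis, Protocol 3.5 and 4.3, Protocol Table 1 with its footnote 3, SAP 2.2.1, and SAP Table 1 with its footnote 3. Under 4.3 it also applies to subjects who stop study drug early.

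**End of AE capture.** Protocol 7.1 and Table 1 footnote 6 run AE collection "through 30 days after the last dose of study drug or last study visit, whichever is later". Protocol 7.4.4 sets the SAE period from "signing of the ICF through 30 days after the last administration of study drug or last study visit, whichever is later". SAP 9.2 counts events as treatment-emergent "up to 30 days after date of last dose or last study visit, whichever is later".

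**How AEs are elicited.** Protocol 7.1: "At each visit the Investigator will ask the subject a nonspecific question".

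**What follows EOS.** Protocol Table 1 footnote 3: "Two additional evaluations are to be conducted beyond this time point, see Footnotes 18 and 23". Footnote 18 is the vital-status call; Protocol 6.1.5 reads "Conduct a vital status telephone call approximately 3 months after the" subject's last study visit, with repeats about every 3 months. Footnote 23 is a pregnancy test at 90 (±5) days in women of childbearing potential. Protocol 4.3 adds a serum sample 3 months after EOS, only after a suspected immunologic reaction and only if the subject agrees to return.

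**The concern.** The visit window is symmetric about day 30, but the AE period has day 30 as its earliest possible end. A late EOS visit extends the period. An early one does not shorten it, so the last AE question is asked before the period is over.

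AE frequency and severity are part of the primary endpoint (Protocol 3.2.1, SAP 2.3.1). For the last few days, ascertainment would depend on where in its window the EOS visit fell and on whether the subject volunteers events. A possible back-up stops at the same point. Protocol 7.1 notes that newly prescribed or as-needed medication may point to an AE, but concomitant medications are recorded only up to EOS (Protocol 5.6, Table 1 footnote 5).

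**Working it through.** The documents give no figure on this point, so there is none to reproduce. The check is day arithmetic.

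**Inputs**
- EOS day *d* after the last dose: 25 to 35, which is 11 permitted days (Protocol 6.1.3).
- End of AE, SAE and TEAE period: max(30, *d*) (Protocol 7.1 and 7.4.4, SAP 9.2).
- Last scheduled AE question: day *d*.
- Dosing: up to 36 infusions, nominally 28 days apart (Protocol 6.1.2).

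**Gap per subject** = max(30, *d*) − *d* = max(0, 30 − *d*)

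| EOS day | 25 | 26 | 27 | 28 | 29 | 30 to 35 |
|---|---|---|---|---|---|---|
| Days without a scheduled AE question | 5 | 4 | 3 | 2 | 1 | 0 |

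**Size**
- Largest gap: 5/30 = 17% of the post-dose days.
- Permitted days that create a gap: 5 of 11 (45%).
- Mean gap if EOS days are evenly spread (assumption): (5+4+3+2+1)/11 = 15/11 = 1.4 days over all subjects, or 15/5 = 3 days among those affected. The documents give no distribution. The mean could lie anywhere from 0 (every EOS on or after day 30) to 5 days (every EOS on day 25).
- Share of the time from first OLE dose to day 30 after the last: a full course is 35 × 28 + 30 = 1010 days, so the worst case is 5/1010 = 0.5%. For a subject who stops after one infusion it is 5/30 = 17%.

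**Could a later contact fill the gap?** Taking 3 months as about 91 days, the first vital-status call falls at about day 25 + 91 = 116 to 35 + 91 = 126. The pregnancy test falls on days 85 to 95. Both come well after day 30, and neither is specified to include an AE question.

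**After the fix.** If the last AE enquiry takes place on day max(*d*, 30), the gap is max(0, 30 − max(*d*, 30)) = 0 for every permitted EOS day.

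**The case against.** The strongest reply is that the plan is coherent as written and that little is lost. The investigator's duty to report runs to at least day 30 whatever the EOS date, so volunteered events are still recorded. SAEs are due within 24 hours of discovery, and those that surface after the period are forwarded if possibly related (Protocol 7.4.4). Vital-status calls find deaths. What is missing is a prompt, not the obligation. All of this stands, and it limits the exposure to new, non-serious, unvolunteered events on at most five days. It does not supply the missing prompt.

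A reader might infer two stronger points. The documents support neither.

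- *Every subject has 30 unprompted days after EOS.* This needs the 30 days to be counted from the last visit as well as from the last dose. Dosing takes place at a visit, so the last visit can never precede the last dose. On that reading the later-of clause would do no work. It has a purpose only if the period ends at the later of last dose plus 30 days and the visit itself.
- *The SAP treats every subject as observed through day 30.* SAP 9.2 only defines which events count as TEAEs. Crude rates divide by subjects exposed (SAP 9.2.1.1). The life-table rates use exposure intervals and reduce the risk set as subjects leave (SAP 9.2.1.2). Neither assigns everyone follow-up to day 30.

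It is also fair to say that SAP Section 11 records the discontinuation of the NEOD001 program, which reduces the practical return from an amendment.

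**Conclusion.** The point holds as a minor gap in primary-endpoint ascertainment. For EOS visits on days 25 to 29, the last scheduled AE question comes 1 to 5 days before the reporting period closes, and no later contact is specified to ask about AEs. The average of 1.4 days rests on evenly spread EOS days. The 0.5% ceiling rests on a full 36-infusion course at exact 28-day intervals. Both results assume that no manual outside the protocol and SAP adds an AE contact. No effect on any TEAE rate has been shown, and any effect is likely small. The case for acting is that the remedy is cheap.

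**What to change.** Choose one:

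- **One-sided window.** Make EOS 30 (+5) days after the last dose in the protocol synopsis, 3.5, 4.3, 6.1.3 and Table 1 with footnote 3, and in SAP 2.2.1 and SAP Table 1 with its footnote 3. The AE question at EOS then never precedes day 30.
- **Added contact.** Keep ±5 days and require a documented AE telephone contact on or after day 30 for any subject whose EOS visit took place before day 30.

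The first costs sites five days of early scheduling flexibility and moves the other EOS assessments with the visit. The second costs one short call for some subjects. Either needs a protocol amendment, which must be notified to the IRB/IEC and may need its approval (Protocol 10.6).

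For subjects already past EOS, neither change helps. Reporting the days from last dose to EOS would show how large the gap actually was.
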